1. SUMMARY

Title of the Study : Investigation of the Effect of Prehabilitation on Patient Outcomes in Frail Patients Planned for Elective Coronary Artery Bypass Graft

Rationale : To see the effect of preoperative routine and improved practices on the patient after surgery.

Purpose : The purpose of the research is, To determine the effect of prehabilitation care on patient outcomes.

Objective : To evaluate the effect of preoperative prehabilitation on patient outcomes and contribute to the literature.

Population : Frail patients scheduled for elective coronary artery bypass grafting at the University of Health Sciences, Istanbul Mehmet Akif Ersoy Thoracic and Cardiovascular Surgery Training and Research Hospital.

Number of Volunteers : The sample calculation of the study was made using Power (G-power) analysis, and the minimum sample size was calculated as 30 patients for both groups, while the Type I error amount was 0.05 and the power of the test was 0.80 ($\alpha=0.05$, $1-\beta=0.80$).

Research Design : The study was planned as a randomized controlled trial.

Procedure : After obtaining institutional approval, the study will continue until the sample size is reached with patients who meet the criteria. Patients identified with the preoperative mini mental test and frailty scale will be administered a patient information form, mini nutritional test, Charlson Comorbidity Index, and Duke activity status index 3-4 weeks before surgery in the intervention group, and 1 day before surgery in the control group. Before postoperative discharge, the appropriate section of the patient information form and the Clavien Dindo classification will be administered and recorded. On the 30th

postoperative day, the mini nutritional test, Duke activity status index, activities of daily living scale, and postoperative recovery index will be administered and recorded.

Research Duration : After obtaining institutional permission, the study will continue until the sample size is reached on patients who meet the criteria.

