9. RESEARCH METHOD

Data for the study will be collected in two stages. In stage 1, patients will be visited before surgery (3-4 weeks before for the intervention group, 1 day before for the control group) and informed about the researchers and the study. Patients who agree to participate and meet the inclusion criteria will be included in the study. Patients will be interviewed face-to-face, and they will complete a patient information form prepared by the researchers based on literature, a mini nutritional test, a 6-minute walk test, and the Borg scale. The intervention group will receive prehabilitation, while the control group will receive routine procedures. Postoperatively, patients will complete a patient information form before discharge, and on the 30th day after surgery, a mini nutritional test, an activities of daily living scale, a postoperative recovery index, a 6-minute walk test, and the Borg scale.

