12. PROCEDURE TO FOLLOW

The study was planned as a randomized controlled trial to be conducted at the cardiovascular surgery clinic of the Istanbul Mehmet Akif Ersoy Thoracic and Cardiovascular Surgery Training and Research Hospital. Patients meeting the sample selection criteria will be included in two groups. Data will be collected using a patient information form, mini nutritional test, Borg scale, activities of daily living scale, and postoperative recovery index. A 6-minute walk test will be administered and recorded. All data will be collected by the researchers.

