13. EVALUATION AND PARAMETERS TO BE RECORDED

Patients will be interviewed face-to-face and a "Patient Information Form," prepared by the researchers based on literature, will be completed. A mini mental test and frailty scale will be used to select patients. A preoperative mini nutritional test, comorbidity scale, 6-minute walk test, and Borg scale will be used for both groups. A patient information form and complication classification will be completed before discharge. On the 30th postoperative day, a mini nutritional test, activities of daily living scale, postoperative recovery index, 6-minute walk test, and Borg scale will be used.

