15. STATISTICS

The data obtained in the study will be analyzed using SPSS 25.0. Descriptive statistical methods such as number, percentage, mean, and standard deviation will be used in the data analysis. Based on the results, the data will be analyzed using relevant tests (t-test, chi-square, Man-Whitney U, Fisher's exact, and regression analysis).

H0: Prehabilitation does not affect patient outcomes in fragile cases undergoing elective coronary artery bypass grafting.

H1: Prehabilitation affects patient outcomes in fragile cases undergoing elective coronary artery bypass grafting.

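### Complications are graded only up to discharge, although both arms are already assessed on day 30: a coherent in-hospital endpoint that could cheaply gain a fixed 30-day window

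*Protocol*

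**What the plan says.** Two places in the protocol give complication grading a time, and they agree.

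- Section 1 (Procedure): "Before postoperative discharge, the appropriate section of the patient information form and the Clavien Dindo classification will be administered and recorded".
- Section 13: "A patient information form and complication classification will be completed before discharge".

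Three places list what is done on day 30.

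- Section 1: "postoperative day, the mini nutritional test, Duke activity status index, activities of daily living scale, and postoperative recovery index will be administered and recorded".
- Section 9: "on the 30th day after surgery, a mini nutritional test, an activities of daily living scale, a postoperative recovery index, a 6-minute walk test", followed by the Borg scale.
- Section 13: "On the 30th postoperative day, a mini nutritional test, activities of daily living scale, postoperative recovery index, 6-minute walk test, and Borg scale".

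None of these lists names the Clavien-Dindo classification, complications, readmission or death. Section 12 lists instruments without times and names no complication tool. The patient information form is scheduled before surgery and before discharge, not on day 30.

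The alternative hypothesis in Section 15 is general: "Prehabilitation affects patient outcomes in fragile cases undergoing elective coronary artery bypass grafting". Section 8 plans 30 patients per group.

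**The concern.** The nutrition, function and recovery measures are taken at a fixed time, day 30, in every patient. Complications are followed only to discharge, so their window is as long as the hospital stay and differs from patient to patient. A complication, readmission or death between discharge and day 30 has no scheduled place in the data.

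The hypothesis does not limit outcomes to the stay, and the text available does not label the complication endpoint as in-hospital. A reader of the results could take it for a 30-day rate. With 30 patients per arm, a few unrecorded patients make up a visible share of the information on complications. The collection window has to be set in the protocol, because an analysis plan cannot recover events that nobody recorded.

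**Working it through.** **The schedule, side by side**

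| Section | Before discharge | Day 30 |
|---|---|---|
| 1 | Information form, Clavien-Dindo | Nutrition, Duke index, daily living, recovery index |
| 9 | Information form | Nutrition, daily living, recovery index, 6-minute walk, Borg |
| 13 | Information form, complication classification | Nutrition, daily living, recovery index, 6-minute walk, Borg |

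Complications appear only in the discharge column. The protocol contains no figure on this point to reproduce.

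**Inputs for the size.** From the protocol: 30 per arm and alpha 0.05 (taken as two-sided, since sidedness is not stated). Assumed, because the protocol gives none of them: 30-day risk R of 30-50%; a share f of 60-80% of events by day 5, with the rest spread evenly to day 30; stay of 6-10 days.

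**Share captured at discharge:** c = f + (1 − f) × (stay − 5)/25.

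- f = 0.6, 6 days: 0.6 + 0.4 × 1/25 = 0.616
- f = 0.6, 10 days: 0.6 + 0.4 × 5/25 = 0.680
- f = 0.8, 6 days: 0.8 + 0.2 × 1/25 = 0.808
- f = 0.8, 10 days: 0.8 + 0.2 × 5/25 = 0.840

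**Missed at discharge if each event is a different patient:** R × (1 − c).

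- Lowest: 0.30 × 0.160 = 4.8 points; × 30 = 1.4 patients.
- Highest: 0.50 × 0.384 = 19.2 points; × 30 = 5.8 patients.

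**Allowing several events per patient.** That product counts events as patients. If events follow a Poisson process with the same R and c, the risk seen at discharge is 1 − (1 − R)^c, and the loss is R minus that.

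- Lowest: 0.30 − (1 − 0.70^0.840) = 4.1 points, 1.2 patients.
- Highest: 0.50 − (1 − 0.50^0.616) = 15.2 points, 4.6 patients.

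Together this gives about 4-19 points, or roughly 1-6 of 30 patients in an arm with risk R. Clustering in the same patients, or later look-up in the hospital record, lowers it further.

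**Power** (exact binomial enumeration, 30 per arm, two-sided 0.05, uncorrected chi-square, equal stay, assumed halving of risk). The in-hospital comparison is Rc against Rc/2. The 30-day comparison is R against R/2 if the effect persists after discharge, and R against Rc/2 + R(1 − c) if it is confined to the stay.

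| R | c | In-hospital | 30-day, effect persists | 30-day, effect in stay only |
|---|---|---|---|---|
| 50% | 0.616 | 0.290 | 0.516 | 0.226 |
| 50% | 0.840 | 0.415 | 0.516 | 0.382 |
| 30% | 0.616 | 0.183 | 0.281 | 0.127 |
| 30% | 0.840 | 0.234 | 0.281 | 0.205 |

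The direction of the change depends on whether the effect outlasts the stay, which the protocol does not say.

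**Unequal stay.** With equal true risk and stays of 6 against 8 days or 7 against 10 days, the difference created by the window alone is R × (1 − f) × (difference in stay)/25. It runs from 0.30 × 0.2 × 2/25 = 0.5 points to 0.50 × 0.4 × 3/25 = 2.4 points. The rejection rate stays at 0.049-0.052.

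**The case against.** The strongest reply is that nothing here is wrong. Sections 1 and 13 agree, and grading in-hospital complications at discharge is a legitimate choice that can rest on the inpatient record. The general wording of the hypothesis does not promise 30-day capture. No primary outcome is named in the text available, so the weight of this endpoint is unknown. All of this stands, and it is why the point is a suggestion and not an error.

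Second, much of the loss may be recoverable. The trial runs at one hospital ("The study was planned as a randomized controlled trial to be conducted at the cardiovascular surgery clinic"), so readmissions there could be looked up, and deaths would usually come to light at the day-30 contact. This also stands in part. But look-up that nobody planned is not systematic, and it misses events treated elsewhere.

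Third, a day-30 update has its own weakness. It leans partly on patient recall, and Section 12 says "All data will be collected by the researchers", so the two arms might be questioned differently. Fixed questions reduce this but do not remove it.

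Two stronger readings are tempting. A reader might infer that stopping at discharge biases the comparison between arms. Under the assumed timing, the distortion from unequal stay is 0.5-2.4 points with no inflation of type I error. A reader might also infer that a 30-day window would raise power. That holds only if the effect persists after discharge; if it is confined to the stay, power falls. The documents support neither inference.

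Finally, Section 14 and the contents of the patient information form and recovery index are not in the text available, so the point concerns only what can be read.

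**Conclusion.** The observation holds: in the text available, complications are graded only before discharge, and no day-30 list names complications, readmission or death. This is a coherent in-hospital endpoint with a variable window, not a mistake. What is lost is systematic information on events after discharge: about 4-19 points, or roughly 1-6 of 30 patients per arm. That range rests wholly on the assumed 30-day risk and on 62-84% of events occurring before discharge.

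The benefit of a change is completeness and a fixed window comparable with the other day-30 outcomes. It is neither a demonstrated power gain nor the removal of a bias. For 50% against 25%, the 30-day window moves power from 0.29-0.42 to 0.52 if the effect persists, but to 0.23-0.38 if it is confined to the stay. The in-hospital result must therefore be kept alongside it. Severity: minor, a cheap improvement.

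**What to change.** In Sections 1, 9 and 13:

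1. Keep the grading at discharge and label it in-hospital complications.
2. At the existing day-30 contact, update the worst Clavien-Dindo grade from surgery to postoperative day 30, including readmission and death.
3. Take the update from the hospital record and from the same fixed questions in both arms.
4. Report both windows.

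The cost is one extra form section at a contact already planned for both arms. What remains is some reliance on recall, some events treated elsewhere that may still be missed, and collection by the researchers themselves. Patient care does not change.

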2. ABBREVIATIONS

3. WORKING SCHEDULE AND DURATION

Obtaining ethics committee approval	May 27, 2025	- Data collection	May 28, 2025	- Literature review	January 1, 2026	- Writing phase of the research	January 1, 2026	- Analysis	April 1, 2026	- Analysis interpretation	April 2026	- Discussing analyses	May 2026	- Writing and presenting research results	May 2026
-------------------------------------	--------------	-------------------	--------------	---------------------	-----------------	---------------------------------	-----------------	------------	---------------	---------------------------	------------	-----------------------	----------	---	----------

4. RATIONALE / IMPORTANCE AND CONTRIBUTION OF THE RESEARCH

Frailty is multifactorial, making it difficult to estimate its prevalence; older age, female gender, unhealthy lifestyle, and low economic status have been identified as potential risk factors. Social factors such as marital status, smoking history, social isolation, and low education levels also place individuals at risk (Dent, E., et al. 2019; Dent, E., et al. 2019). Research suggests that frailty increases with the number of health deficits and the presence of multiple comorbidities. Higher rates of frailty have been documented in patients diagnosed with diabetes, respiratory disease, stroke, dementia, multiple sclerosis, connective tissue disease, osteoarthritis, and chronic fatigue syndrome (Liu, X., et al. 2019).

There is currently no recommendation to routinely screen for frailty. However, to optimize care and communicate appropriately with families, clinicians may need to identify at-risk patients and those who may already be frail (Hsieh, T.J., et al. 2019). Frailty is not defined by a single patient-reported symptom or physical examination finding, and no single laboratory test or imaging study can diagnose frailty. Instead, frailty is assessed through a comprehensive history and physical examination, focusing on several key elements (Arrieta, H., et al. 2019). A patient considered frail should be assessed using validated frailty assessment tools. A suggested approach to optimizing preoperative care is presented, which includes recommendations for identifying underlying physical disability, malnutrition, cognitive dysfunction, and mental health diagnoses following frailty assessment (Braun, T., et al. 2019).

The fundamental concept of prehabilitation is to increase an individual's functional capacity to withstand an anticipated injury. It embodies the idea of a proactive approach to rehabilitation, as opposed to the reactive approach commonly used in rehabilitation (Esser, T., Zimmer, P., Schier, R. 2022). While the initial prehabilitation model was limited to physical training, it has evolved into a multimodal entity that, in addition to exercise programs, includes nutritional optimization, psychosocial preparation, and smoking cessation. Over the past decade, there has been an increasing effort to coincide prehabilitation with surgery, as surgery is rightfully perceived as a stressor for human structural and physiological functions (McIsaac, D.I., et al. 2022).

5. PURPOSES

The aim of the study is to determine the effect of prehabilitation care on patient outcomes.

6. EXPECTED BENEFITS FROM THE RESEARCH

Frailty is an increasingly recognized risk factor for surgery. The degree of frailty and how it may impact postoperative recovery profiles are unclear. Preoperative frailty may predispose patients to poorer outcomes in cardiac surgery; however, there are limited data on how preoperative frailty impacts patient outcomes through prehabilitation practices.

7. TYPE OF RESEARCH

Prospective **Retrospective**

Descriptive studies

Descriptive

Analytical studies

Observational studies

Cross-sectional studies

Cohort studies (prospective, retrospective, bidirectional)

Case-control studies

Qualitative analyses

Survey studies

Case-control studies

Randomized

Non-Randomized

Self-Control (Paired Series)

Cross-Checked

Externally Controlled

Those Without a Control Group

Meta-Analyses

Methodological Research

Experimental Studies (No Direct Intervention, No Drug or Medical Device Studies)

In vitro studies

Studies to be conducted with blood, urine and pathology collection materials

Cell and tissue culture studies

Studies with genetic material that are for identification purposes and are not included in gene therapy clinical trials

8. POPULATION TO BE STUDIED

How was the sample size decided: It was decided by G-power analysis.

Number of volunteers planned to be included: 30+30

Volunteer Age Range: 60+

- Agreeing to participate in the research,
- Undergoing elective open coronary artery bypass grafting
- Being 60 years old or older,
- Being in the frail patient status as a result of the FRIED Frailty Scale,
- Being able to communicate in Turkish.

Exclusion Criteria: Patients whose surgery has been postponed and those whose mini mental test result is 23 or below will not be included.

Gender: Male and female

Are there any vulnerable groups/individuals (children, disabled people, unconscious individuals) planned to be included?

Yes No

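### Planned enrolment of 30+30 equals the stated minimum for 0.80 power, so the 0.80 holds only if every included patient is evaluated

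*Protocol*

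**What the plan says.** The Summary (Section 1, Number of Volunteers) reports that "the minimum sample size was calculated as 30 patients for both groups". The same sentence sets alpha at 0.05 and puts power at 0.80. Section 8 says of the method only that "It was decided by G-power analysis", and gives the target as "Number of volunteers planned to be included: 30+30".

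Section 9 fixes when a patient counts as included. At the visit before surgery, 3-4 weeks ahead for the intervention group and 1 day ahead for the control group, "Patients who agree to participate and meet the inclusion criteria will be included in the study". The nutritional test, walk test and Borg scale are then repeated on day 30 after surgery, when the daily-living scale and the recovery index are also taken (Sections 9 and 13). The complication classification and part of the patient information form are completed before discharge.

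Two further statements bear on who counts. The exclusion criteria in Section 8 say "Patients whose surgery has been postponed and those whose mini mental test result is 23 or below will not be included". The Summary says "the study will continue until the sample size is reached with patients who meet the criteria".

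**The concern.** Section 8 and Section 9 both speak of patients being included, and Section 9 ties that to eligibility and agreement before surgery. On that reading 30+30 is a count of enrolled patients. A power statement, however, describes the number analysed. When the number enrolled equals the calculated minimum, any patient without the outcome takes the analysis below the protocol's own minimum.

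Loss is plausible here. The patients are frail, aged 60 or over and having open bypass surgery, and several outcomes need them to be assessed on day 30. Intervention patients are also included 3-4 weeks before surgery, against 1 day for controls, so they have longer in which to be lost, and the loss may differ between groups.

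What is at stake is interpretation. A null result would be read as coming from a trial with 80% power, when power at the analysed number could be several points lower.

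**Working it through.** **Inputs from the protocol.** Alpha 0.05 and power 0.80 (Section 1); minimum 30, taken as per group because Section 8 plans 30+30; 1:1 allocation (Section 8).

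**Inputs the protocol does not give.** Effect size, standard deviation, powered outcome, test, sidedness and loss rate. The figure of 30 therefore cannot be reproduced. I assume a two-sided two-sample t-test and solve backwards for the effect that 30 per group implies. Loss rates are shown as a range.

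**Formula.** With n per group and standardised difference d, the degrees of freedom are 2n − 2 and the noncentrality is d × √(n/2). Power is the probability that a noncentral t variable with these parameters falls beyond ± the 97.5% point of the central t.

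**Step 1: implied effect.** With n = 30 there are 58 degrees of freedom and the critical value is 2.002. Power of 0.80 needs a noncentrality of 2.849, so d = 2.849 / √15 = 0.736.

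**Step 2: power with d held at 0.736, and the difference detectable with power 0.80.**

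| Evaluable per group | Loss | Noncentrality | Power | Detectable difference (SD) |
|---|---|---|---|---|
| 30 | none | 2.849 | 0.800 | 0.736 |
| 29 | 1 patient | 2.801 | 0.786 | 0.749 |
| 28 | 2 patients | 2.752 | 0.771 | 0.762 |
| 27 | 10% | 2.703 | 0.756 | 0.777 |
| 24 | 20% | 2.548 | 0.704 | 0.826 |

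**Step 3: sensitivity.**

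- Loss of three patients in the intervention group only (27 against 30) gives power 0.778.
- A one-sided test implies d = 0.650, with power 0.761 at 10% loss and 0.716 at 20%. The pattern does not depend on sidedness.
- If 30 in the Summary is the total (15 per group), the implied d is 1.06. The planned 30+30 then has power 0.98, and 0.95 with 24 per group. On that reading there is no shortfall.

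**The case against.** **The recruitment rule may already cover this.** The Summary says "the study will continue until the sample size is reached with patients who meet the criteria", and Section 8 excludes postponed surgery. Together these can mean that a postponed patient does not count and recruitment carries on past them. That is a fair reading, and it would reduce the loss. It does not remove it: the rule speaks of meeting the criteria, not of completing day 30, so deaths and missed visits remain. Nor does the protocol say what happens when surgery is postponed after a patient has been included.

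**The powered outcome may not be a day-30 one.** Complications are classified before discharge, and nothing ties the sample size to a later outcome. This stands. For an in-hospital outcome, missed day-30 visits would not matter.

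**No figure is shown to be miscalculated, and the loss rate is assumed.** Also true. Every magnitude above rests on a back-solved effect. The missing effect size and outcome are the larger weakness, because without them the 0.80 cannot be checked at all.

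**An allowance or replacement rule might exist elsewhere.** Section 14 is not in the available text, so its absence cannot be confirmed. The point is limited to the sample-size statements as they stand.

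**Two stronger inferences are not supported.** A reader might conclude that the trial fails to deliver 0.80 power. The documents do not establish that, since they give no loss rate and may allow replacement of postponed patients. A reader might also take the phrase "the minimum sample size was calculated as 30 patients for both groups" to mean 30 in total and infer that power is much worse. The opposite follows: the implied effect would be larger and 30+30 would be ample. The 30+30 in Section 8 makes the per-group reading the natural one, so this is loose wording and not a clear contradiction.

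**Conclusion.** The point holds in a conditional form. On the per-group reading, the enrolled number equals the stated minimum, with no visible margin for loss between inclusion and outcome. The 0.80 is then a best case, reached only if every included patient is evaluated.

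Under the assumed t-test and d = 0.736, the cost is about 3 points of power with two patients lost per group, 4 to 5 points at 10% loss and about 10 points at 20%. Equivalently, the difference detectable with 80% power grows from 0.74 SD to 0.78 SD and 0.83 SD at 10% and 20% loss. The loss rates are illustrations, not predictions. The shortfall is smaller if postponed patients are replaced, and also if the powered outcome is recorded before discharge. This is a moderate matter of stating the design's power accurately, not an error in a calculation.

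**What to change.** In Sections 1 and 8:

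- Write 30 patients in each group, 60 in total, enrolled. This settles both per group versus total and enrolled versus evaluable.
- Name the outcome, the test and the effect size that were entered in G*Power.
- Replace the unconditional 0.80 with the power at the number expected to be evaluable for that outcome, and state the loss rate assumed. The figures of 0.76 at 27 per group and 0.70 at 24 show the form of such a statement. The sponsor should recompute them from its own effect size.
- State whether a patient whose surgery is postponed after inclusion still counts toward the 30.

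Recruiting until 30 per group are evaluable on day 30 is not a good substitute. It would replace randomised patients because of events after randomisation, including death, and so weaken the randomised comparison.

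The cost is protocol wording only, and the stated power becomes slightly less favourable. No extra enrolment is needed. If the sponsor would rather keep 0.80 at the analysed number, the route is to inflate at the outset by n / (1 − loss): 30 / 0.90 = 33.3, so 34 per group at 10% loss, and 30 / 0.80 = 37.5, so 38 per group at 20%.

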11. RESEARCH DESIGN / METHOD

The study was planned as a randomized controlled trial.

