17. INFORMED VOLUNTARY CONSENT

Before the surgery, the patient will be visited in the room, informed and consent will be obtained before data collection.

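### Section 8 sets no time-to-surgery condition, so patients less than 3 weeks from surgery are eligible for a trial whose intervention-group visit falls 3-4 weeks before surgery

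*Protocol*

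**What the plan says.** Section 8 lists five inclusion criteria: consent, age 60 or over, frailty on the FRIED scale, ability to communicate in Turkish, and "Undergoing elective open coronary artery bypass grafting". The exclusions are "Patients whose surgery has been postponed and those whose mini mental test result is 23 or below will not be included". The Section 1 population statement, "Frail patients scheduled for elective coronary artery bypass grafting", likewise carries no interval to surgery.

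Section 9 sets the first visit, at which patients are told about the study, as "3-4 weeks before for the intervention group, 1 day before for the control group". It then states: "Patients who agree to participate and meet the inclusion criteria will be included in the study". Section 1 gives the same split for the first assessments: "3-4 weeks before surgery in the intervention group, and 1 day before surgery in the control group".

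Section 17 adds, on consent: "Before the surgery, the patient will be visited in the room". Section 11 gives the design: "The study was planned as a randomized controlled trial". No section shown says at what point allocation is drawn.

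**The concern.** A randomised comparison needs both arms to come from patients who could have received either allocation. Here the eligibility rule and the visit schedule do not fit together. The schedule requires intervention patients to be known to the study at least 3 weeks before surgery. The eligibility rule does not, and the control schedule needs only one day.

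What is at stake is comparability. Waiting time for elective surgery may reflect urgency and other features of the patient or the referral. If the rules let short-wait patients into one arm and not the other, the arms can differ in waiting time and in whatever determined it, and that difference cannot be separated from the effect of prehabilitation. If such patients enter both arms, some of the intervention arm cannot have the intervention as scheduled.

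**Working it through.** **Step 1: is there a lead-time condition anywhere?** Neither the five inclusion criteria nor the two exclusions in Section 8 contains one. The postponement exclusion concerns operations that are moved later; it does not screen out short waits. The word elective implies planning but guarantees no 3-week notice. Sections 1, 9, 12 and 13 add none.

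**Step 2: apply the rules to one case.** Take a frail, consenting, Turkish-speaking patient aged 70, cognitively eligible, listed for elective open bypass surgery in 10 days.

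| Rule | Result |
|---|---|
| Section 8 criteria | All met |
| Intervention visit, 3-4 weeks before surgery | Impossible; 10 days remain |
| Control visit, 1 day before surgery | Possible |

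**Step 3: follow each possible timing of allocation.** Let p be the share of eligible patients first identified less than 3 weeks before surgery.

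- *Inclusion at the visit, as Section 9 reads.* Short-wait patients enter only as controls. If controls are drawn from all eligible patients, about 30p of the 30 controls are short-wait: 0, 3, 6 and 9 at p = 0, 10, 20 and 30%. No intervention patient seen on schedule has such a wait. If short-wait and longer-wait controls differ in mean outcome by δ, the control mean shifts by pδ and the estimated effect is biased by that amount. Neither p nor δ is given.
- *Allocation earlier, short-wait patients kept.* If they gain nothing, the mean effect is multiplied by (1 − p).
- *Allocation earlier, short-wait patients dropped from intervention.* The intervention arm holds only longer-wait patients while the control arm keeps its mix, so the shift of pδ returns.

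**Step 4: size of the dilution branch.** Inputs from the protocol: alpha 0.05 and power 0.80 (Section 1), 30 + 30 patients (Section 8). No effect size or standard deviation is given, so the 30 per group cannot be reproduced forward. Solving backwards, two-sided, it corresponds to a standardised difference of about 0.72 (normal approximation, (1.960 + 0.842) × √(2/30)) or 0.74 (t-test).

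Under the normal approximation the result does not need that difference. The design non-centrality is 1.960 + 0.842 = 2.802, and with the effect multiplied by (1 − p) and the variance unchanged,

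power = Φ(2.802 × (1 − p) − 1.960).

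| p | Argument of Φ | Power |
|---|---|---|
| 0 | 0.842 | 0.80 |
| 10% | 0.562 | 0.71 |
| 20% | 0.282 | 0.61 |
| 30% | 0.001 | 0.50 |

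A t-test calculation at a standardised difference of 0.736 agrees: 0.713 at p = 10% and 0.557 at p = 25%, where the formula gives Φ(0.14) = 0.56.

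**The case against.** The strongest objection is that the problem is not Section 8's alone. It arises because the two groups are approached at different times. If both were approached and allocated at the same visit 3-4 weeks before surgery, the schedule itself would impose the lead time. That stands, and it is why the remedy must cover the timing as well as the criterion. It does not remove the point: if patients are allocated at listing, aligning the assessments would still leave eligible some who cannot follow the intervention schedule.

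Four stronger readings are tempting and are not supported.

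- *Short-wait patients can enter only as controls.* This follows if Section 9 is taken literally. Section 8 does not say it, the trial is declared randomised, and the time of allocation is not stated.
- *The intervention arm will lose 3, 6 or 9 patients.* Section 1 says the study continues until the sample size is reached, so dropped patients could be replaced. What remains is selection, not a demonstrated loss of numbers.
- *Section 17 shows that recruitment happens close to surgery.* It says consent is taken in the patient's room before surgery and before data collection. It gives no interval.
- *A 3-week criterion in Section 8 is enough.* If eligibility is checked at the Section 9 visit, 1 day before surgery for controls, that criterion would exclude every control.

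The power figures are also open to challenge. The share p is assumed, 0.80 is tied to no stated endpoint or effect size, and zero benefit is a harsh assumption for someone seen, say, 20 days before surgery. They illustrate; they do not measure this trial.

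**Conclusion.** The point holds as an inconsistency between eligibility and schedule. Section 8 admits patients who cannot have the intervention visit that Sections 1 and 9 prescribe, and this is so whenever allocation is drawn. The consequence depends on that timing: confounding of waiting time with treatment if inclusion follows Section 9, otherwise dilution or one-sided selection.

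The size is unknown. With p near zero the practical effect is negligible. With p of 10 to 30% and no benefit in those patients, nominal power of 0.80 would be 0.71 to 0.50 in the dilution branch. Bias in the other branches is p times an unknown outcome difference, with unknown direction. Section 14 is not in the text available, so a lead-time condition there could not be ruled out. The change should be made, since an analysis cannot reliably restore comparability once the arms have been recruited from different waiting times.

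**What to change.** Reconcile Sections 1, 8, 9 and 17 in one amendment:

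- **Sections 1 and 9:** identify, inform and check eligibility of patients for both arms at the same point before surgery. The contact 1 day before surgery may remain for controls but must no longer be their point of inclusion.
- **Section 8:** add one lead-time criterion, the same for both arms, consistent with the protocol's own 3-4 week window. The investigators set the exact interval.
- **Allocation:** state that it is drawn only after this criterion has been checked, and that patients who do not meet it enter neither arm.
- **Section 17:** place consent at that common visit.

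The cost is more than one added line: controls must be approached weeks earlier than now planned, and recruitment may be slower. The result will apply only to patients with the required lead time, who are the only ones able to follow the intervention schedule as written.
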